## 2.3. Study Design

Overview of Study Design and Key Features	

The diagram illustrates the study design. Part 1 (SAD) consists of two cohorts, Cohort 1 and Cohort 2, each with four periods of treatment. Cohort 1 doses are 1 mg, 10 mg, 100 mg, and 400 mg. Cohort 2 doses are 3 mg, 30 mg, 200 mg, and 700 mg. Part 2 (MAD) consists of five cohorts: Cohort 3 (50 mg QD), Cohort 4 (100 mg QD), Cohort 5 (200 mg QD), Cohort 6 (320 mg QD), and an Expansion Cohort (200 mg QD). All cohorts in Part 2 have 14 days of treatment and n=8 participants (A/P=6/2), except for the Expansion Cohort which has n=24 (A/P=18/6).
	
Design Features	
 
Two part, Phase 1, double-blind (sponsor-unblinded), randomized, placebo controlled, single- and repeat-dose escalation study.
 
 
Part 1 (SAD):
 
 
SAD portion will be conducted in an interlocking fashion with 2 separate cohorts of 8 healthy participants each. Each of these 2 cohorts will contain up to 4 escalating doses of GSK3640254.
 
In each escalating period and Cohort, 6 participants will be randomized to GSK3640254 and 2 participants will be randomized to placebo.
 
Participants in Cohort 1 and Cohort 2 will follow the same randomization strategy with alternating ascending doses with 4-period crossover, placebo-controlled.
 
 
Part 2 (MAD):
 
 
Part 2 consists of 4 ascending repeat-dose cohorts (Cohorts 3 to 6), each with 8 participants (active/PBO=6/2) who will receive a once-daily dose of GSK3640254 or PBO for 14 days.
 
Part 2 also includes an Expansion Cohort which will be conducted at the conclusion of cohort 5.
 
The Expansion Cohort will evaluate the rate of GI intolerability in 24 participants (active/PBO =18/6).
 

Dosing	
Part 1 (SAD):
 
 
The dose for Part 1 Cohort 1 of this study were 1 mg for Period 1, 10 mg for Period 2, 100 mg for Period 3 and 400 mg for Period 4.
 
The dose for Part 1 Cohort 2 of this study will be 3 mg for Period 1, 30 mg for Period 2, 200 mg for Period 3 and 700 mg for Period 4.
 
 
Part 2 (MAD):
 
 
The dose for Part 2 of this study were 50 mg for Cohort 3, 100 mg for Cohort 4, 200 mg for Cohort 5 and the expansion cohort, and 320 mg for cohort 6.
 

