Overview of Study Design and Key Features																																																			
	All doses were administered in fed condition.																																																		
Time & Events	
 
Refer to Appendix 2: Schedule of Activities
 
																																																		
Treatment Assignment	
Part 1 (SAD):
 
 
Participants in either Cohort 1 or Cohort 2 will be assigned to 1 of the 4 treatment sequences in a cross-over, and each participant will receive placebo once.
 
 
  
 Cohort 1	Period 1	Period 2	Period 3	Period 4	
   
 Sequence 1	Placebo	Dose 3	Dose 5	Dose 7	
 
 Sequence 2	Dose 1	Placebo	Dose 5	Dose 7	
 
 Sequence 3	Dose 1	Dose 3	Placebo	Dose 7	
 
 Sequence 4	Dose 1	Dose 3	Dose 5	Placebo	
  
 
  
 Cohort 2	Period 1	Period 2	Period 3	Period 4	
   
 Sequence 1	Placebo	Dose 4	Dose 6	Dose 8	
 
 Sequence 2	Dose 2	Placebo	Dose 6	Dose 8	
 
 Sequence 3	Dose 2	Dose 4	Placebo	Dose 8	
 
 Sequence 4	Dose 2	Dose 4	Dose 6	Placebo	
  
 
Part 2 (MAD):
 
 
In Cohorts 3 to 6, 8 participants per cohort (active/PBO=6/2) will receive a once-daily dose of GSK3640254 or PBO for 14 days.
 
In the Expansion Cohort, 24 participants (active/PBO=18/6) will receive a once-daily dose (200 mg) of GSK3640254 or PBO for 14 days
 
	Cohort 1	Period 1	Period 2	Period 3	Period 4	Sequence 1	Placebo	Dose 3	Dose 5	Dose 7	Sequence 2	Dose 1	Placebo	Dose 5	Dose 7	Sequence 3	Dose 1	Dose 3	Placebo	Dose 7	Sequence 4	Dose 1	Dose 3	Dose 5	Placebo	Cohort 2	Period 1	Period 2	Period 3	Period 4	Sequence 1	Placebo	Dose 4	Dose 6	Dose 8	Sequence 2	Dose 2	Placebo	Dose 6	Dose 8	Sequence 3	Dose 2	Dose 4	Placebo	Dose 8	Sequence 4	Dose 2	Dose 4	Dose 6	Placebo

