**5. CONSIDERATIONS FOR DATA ANALYSES AND DATA HANDLING CONVENTIONS**

**5.1. Study Treatment & Sub-group Display Descriptors**

Treatment Group Descriptions				
RandAll NG		Data Displays for Reporting		
Code	Description	Description	Header	Order in TLF
Part 1				
P/PS	Placebo/Placebo Sentinel	Placebo SD	SD PBO	9
D1/ D1S	GSK3640254 Dose Level 1/ GSK3640254 Dose Level 1 sentinel	GSK3640254 1 mg SD	SD 1mg	1
D2/ D2S	GSK3640254 Dose Level 2/ GSK3640254 Dose Level 2 sentinel	GSK3640254 3 mg SD	SD 3mg	2
D3/ D3S	GSK3640254 Dose Level 3/ GSK3640254 Dose Level 3 sentinel	GSK3640254 10 mg SD	SD 10mg	3
D4/ D4S	GSK3640254 Dose Level 4/ GSK3640254 Dose Level 4 sentinel	GSK3640254 30 mg SD	SD 30mg	4
D5/ D5S	GSK3640254 Dose Level 5/ GSK3640254 Dose Level 5 sentinel	GSK3640254 100 mg SD	SD 100mg	5
D6/ D6S	GSK3640254 Dose Level 6/ GSK3640254 Dose Level 6 sentinel	GSK3640254 200 mg SD	SD 200mg	6
D7/ D7S	GSK3640254 Dose Level 7/ GSK3640254 Dose Level 7 sentinel	GSK3640254 400 mg SD	SD 400mg	7
D8/ D8S	GSK3640254 Dose Level 8/ GSK3640254 Dose Level 8 sentinel	GSK3640254 700 mg SD	SD 700mg	8
Part 2				
RP	Placebo Repeated Dose	Placebo RD	RD PBO	5
R1	GSK3640254 Repeat Dose Level 1	GSK3640254 50 mg RD	RD 50mg	1
R2	GSK3640254 Repeat Dose Level 2	GSK3640254 100 mg RD	RD 100mg	2
R3	GSK3640254 Repeat Dose Level 3	GSK3640254 200 mg RD	RD200 mg	3
R4	GSK3640254 Repeat Dose Level 4	GSK3640254 320 mg RD	RD 320mg	4
R5	GSK3640254 Repeat Dose Level for Expansion Cohort	GSK3640254 200 mg RD	RD200 mg	3

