### 8.1.4.1. Statistical Methodology Specification

#### Dose Proportionality-Power model:

*Part 1, and 2:*

Dose proportionality of GSK3640254 following single-dose administration in Part 1 and following single-dose and repeat-dose administration in Part 2 of the study will be assessed separately using the power model (Smith, 2000) as described below:

$$y = \alpha * dose^{\beta}$$

where y denotes the PK parameter being analyzed [for Part 1: AUC(0-∞), AUC(0-24), and Cmax. For Part 2: AUC(0-24), Cmax on Day1;

AUC(0-τ), Cmax, Cτ on Day 14] . Dose proportionality implies that β=1 and will be assessed by estimating β along with its confidence interval. The exponent, β, in the power model will be estimated by regressing the loge-transformed PK parameter on loge dose.

$$\log(y) = \log(\alpha) + \beta * \log(\text{dose})$$

The power model will be fitted by restricted maximum likelihood (REML) using SAS

Proc Mixed. For Part 1, a power model with subject as the random effect will be fitted. If the model does not converge then a fixed effect power model will be fitted. For Part 2, a fixed effect power model will be fitted. The mean slope will be estimated from the power model and the corresponding 90% confidence interval calculated. Intra-subject CV% calculated from the model will be presented in the table. Point estimates and confidence intervals for the slope will be reported to 4 decimal places with no rounding.

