## **Dose Proportionality-ANOVA Model**

*Part 1, and 2:*

Additionally, dose proportionality may be assessed by pair-wise analysis of variance (ANOVA) using the SAS Mixed model procedure if power model does not show dose proportionality. A reference dose of 3 mg for all parts, and will be used and the other doses would be treated as test dose. PK parameters will be normalized to the reference dose and then log-transformed prior to the analysis. Point estimates and 90% confidence intervals for AUC and Cmax will be reported to 4 decimal places with no rounding. An example of SAS code is also included here for the ANOVA approach.

*ODS output solutionf=stat;*

*Proc Mixed;*

*class treatment; /\* treatments are different dose groups \*/*

*model logdnPKvar = treatment/ddfm=kr;*

*lsmeans treatment; /\* assuming one ref and four test treatments \*/*

*estimate 'test1 vs ref' treatment -1 1 0 0 0 /cl alpha=0.1;*

*estimate 'test2 vs ref' treatment -1 0 1 0 0 /cl alpha=0.1;*

*run;*

Individual and box plot of dose-normalized plasma GSK3640254 PK parameters by treatment will be generated.

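### The dose-proportionality ANOVA names a 3 mg reference that Part 2 never gave, and its Part 1 model leaves out subject in a crossover

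*SAP*

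**What the plan says.** SAP Section 8.1.4.1 (Dose Proportionality-ANOVA Model) covers Parts 1 and 2 and may be used when the power model does not show proportionality. PK parameters are normalised to the reference dose and log-transformed. The reference rule is: "A reference dose of 3 mg for all parts, and will be used and the other doses would be treated as test dose". The example code has treatment as its only effect, "model logdnPKvar = treatment/ddfm=kr", and a comment "assuming one ref and four test treatments".

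The doses are in SAP Section 2.3. For Part 2: "The dose for Part 2 of this study were 50 mg for Cohort 3, 100 mg for Cohort 4, 200 mg for Cohort 5", with 200 mg again in the expansion cohort and 320 mg in Cohort 6. The first repeat-dose group in SAP Section 5.1 is "GSK3640254 50 mg RD". No 3 mg repeat-dose group is listed. In Part 1, Cohort 1 received 1, 10, 100 and 400 mg and Cohort 2 received 3, 30, 200 and 700 mg, and "each participant will receive placebo once".

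The power model in the same section is specified differently: "For Part 1, a power model with subject as the random effect will be fitted". The accumulation and steady-state analyses also carry a random subject effect.

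The planned ANOVA outputs are Table 4.5 and Listing 86 (Part 1), and Tables 4.11 and 4.12 with Listings 91 and 92 (Part 2, Days 1 and 14).

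**The concern.** Dose proportionality is a secondary objective, and this ANOVA is its planned follow-up. Two things go wrong if it is run as written.

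First, the Part 2 comparisons have no reference group. Someone would then have to pick a reference after seeing the data, and the choice affects the ratios reported. Second, in Part 1 the same Cohort 2 participants supply the 3, 30, 200 and 700 mg data, but the model treats every observation as independent. That gives up the precision the crossover was designed to provide, including at 700 mg against 3 mg, where protocol Section 3.2.2 describes a plateau in exposure. Intervals that are too wide make a departure from proportionality harder to see.

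The example contrasts also fit neither part. Part 1 has one reference and seven test doses. Part 2 has four doses in all.

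**Working it through.** The documents give no standard error, power or coverage figure for this ANOVA, so there is nothing of the plan's own to reproduce.

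**Part 2.** Participants on active drug: 6 at 50 mg, 6 at 100 mg, 6 + 18 = 24 at 200 mg, 6 at 320 mg, and 0 at 3 mg. A contrast of any dose with 3 mg needs a 3 mg mean, and none exists. A rank check on the design matrix confirms that 50, 100, 200 and 320 mg against 3 mg are all non-estimable.
- Reference 3 mg: 4 test doses x 2 parameters (AUC, Cmax) x 2 days = 16 contrasts, 0 estimable.
- Reference 50 mg: 3 x 2 x 2 = 12 contrasts, all estimable.

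Dose-normalised means and plots survive, because scaling to 3 mg only multiplies by a constant.

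**Part 1 layout.** Each cohort has 8 participants, 2 per sequence, so there are 6 active observations per dose and 48 in all. The residual df are 48 - 8 = 40. Each participant misses one dose for placebo, so any two doses of a cohort share 8 - 2 - 2 = 4 participants.

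**Contrasts within Cohort 2 (30, 200 and 700 against 3 mg), equal variance across doses.** Let sb² and sw² be the between- and within-subject log-variances, each ln(1 + CV²).
- Variance the planned model assumes: (sb² + sw²) x 2/6 = (sb² + sw²)/3.
- True variance of the same mean difference: (sb² + sw²)/3 - 2 x 4 x sb²/36 = sb²/9 + sw²/3.
- CVw = CVb: ratio (2/3)/(4/9) = 1.50, so the SE ratio is 1.22.
- CVw = CVb/2, for example 12.5% and 25%: sb² = 0.0606 and sw² = 0.0155, so 0.02537/0.01190 = 2.13 and the SE ratio is 1.46.

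These are the two CV ratios used in protocol Table 6. The table adds larger within-subject CVs, at CVb of 25% and 35%. Coverage of the nominal 90% interval is from simulation. The last column compares the planned SE with that of a random-subject model with variances known.

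| CVw/CVb | Planned SE / true SE | Coverage | Planned SE / random-subject SE |
|---|---|---|---|
| 0.5 | 1.45-1.46 | 98% | 2.05-2.11 |
| 1 | 1.22 | 95-96% | 1.35 |
| 1.25 | 1.16-1.17 | 94% | 1.24 |
| 1.5 | 1.13 | 93-94% | 1.17 |
| 2 | 1.08 | 92-93% | 1.10-1.11 |

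**Where the trial probably lies.** No within-subject CV is reported. The Cohort 2 CVs in protocol Table 3 give a rough bound, if between-subject variance is constant and no larger than the smallest total variance.
- Cmax (31, 21, 27, 44%): log-variances 0.0918, 0.0432, 0.0704, 0.1770; mean 0.0956. Within-subject part at least 0.0956 - 0.0432 = 0.0524. CVw is then at least about 1.1 times CVb, and the SE ratios are at most 1.20 (true SE) and 1.30 (random-subject SE).
- AUC(0-inf) (29, 26, 41, 50%): mean 0.1312, minimum 0.0654, difference 0.0658. CVw is at least about 1.0 times CVb, and the ratios are at most 1.22 and 1.35.

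With 6 participants per dose these bounds are noisy.

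**Contrasts across cohorts (1, 10, 100 and 400 against 3 mg).** No participants are shared, so leaving out subject does not bias the variance. Simulated coverage under equal variance is 89-90%.

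**Check with unequal variances.** With the Table 3 Cmax CVs, the pooled log-variance is 0.1418. For 700 against 3 mg at a within-subject correlation of 0.5, the planned variance is 0.1418/3 = 0.0473. The true variance is (0.0918 + 0.1770)/6 - 8 x 0.5 x 0.1274/36 = 0.0306, where 0.1274 = √(0.0918 x 0.1770). The SE ratio is 1.24. At correlations of 0.2 and 0.8 it is 1.10 and 1.46.

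**The case against.** The strongest reply concerns weight. The ANOVA is optional and conditional, no hypotheses are tested, and protocol Section 10.3.2 names only the power model. Tables 4.4, 4.9 and 4.10 serve the objective without it. The Part 2 slip would show itself: a programmer would find no 3 mg group, so no wrong number would reach the report. This stands and limits the importance of the point, but a pre-specified reference is still missing.

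The code is offered as an example, and the text does not exclude a subject effect. Table 4.5 shares its shell with the Part 1 power-model table, and SAP Section 11.5.2 defines a within-subject CV from a model residual, so a subject term may have been intended. That is possible, but neither the ANOVA text nor its code says so, while three neighbouring analyses do. The Part 1 power model also drops subject, but only if the model with it fails to converge. The mismatch of the example contrasts is a minor matter of adapting a template.

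Unequal variance may matter more than the missing subject term. With the Table 3 Cmax CVs and zero correlation, pooling alone gives SE ratios of 1.45, 1.32 and 1.03 for 30, 200 and 700 against 3 mg, and 0.75 for 100 against 3 mg, which is anti-conservative. Leaving out subject multiplies the three same-cohort ratios by 1.07-1.08 at correlation 0.2, 1.20-1.23 at 0.5 and 1.41-1.46 at 0.8. This is fair: a random subject effect does not cure unequal variance.

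Replacement participants, which the protocol allows, would reduce the overlap. With 1 to 3 shared participants the SE ratio is 1.04-1.29 for the CV pairs checked (CVw equal to or half of CVb). It remains above 1.

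**Conclusion.** The point holds. In Part 2 the reference rule cannot be carried out, and this needs no assumption beyond the doses listed in the SAP. In Part 1 the intervals for 30, 200 and 700 against 3 mg are conservative whenever between-subject variance is positive, given four shared participants and equal variance across doses. The inflation of the standard error is 1.22 at equal CVs. The preliminary data suggest that or less, and 1.45-1.46 would require a within-subject CV of half the between-subject CV. The four cross-cohort contrasts are not conservative; leaving out subject costs them at most about one percentage point of coverage under equal variance. This should be corrected, but it touches only an optional analysis of a secondary objective. No primary safety result, escalation rule or sample size depends on it.

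**What to change.** In SAP Section 8.1.4.1:
1. Name a reference for each part from the doses given in that part, and normalise to it: for example, keep 3 mg in Part 1 and use the lowest dose, 50 mg, in Part 2.
2. In the Part 1 ANOVA, add subject to the CLASS statement and fit a random subject effect, as the Part 1 power model does.
3. Rewrite the example ESTIMATE statements for the number of doses and the reference level in each part: eight doses in Part 1, four in Part 2.

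The cost is a few lines of SAP text and SAS code. Data, design and sample size do not change.

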## **Accumulation Ratio Analysis**

Part 2:

An ANOVA with a random effect term for subject and fixed effect terms for day will be performed by dose on the loge-transformed PK parameters (AUC(0- $\tau$ ), C $\tau$ , and Cmax). Day will be treated as a class variable in the model. The accumulation ratio of GSK3640254 will be estimated by calculating the ratio of the geometric least squares (GLS) means of PK parameters between Day 14 and Day 1 for Cohort 3,4,5, 6 and expansion, and the corresponding 90% CI for each dose.

*An example of SAS code is included here.*

*ODS output solutionf=stat;*

*Proc Mixed;*

*by dose;*

*class subject day;*

*model logPKpar = day / ddfm=kr;*

*random subject;*

*lsmeans day;*

*estimate 'Day X vs Day 1' day -1 /cl alpha=0.1;*

*run;*

Comparative plots of individual plasma GSK3640254 PK estimates will be generated by dose group [AUC(0- $\tau$ ), C $\tau$ , and Cmax on Day 14 versus AUC(0-24), C24 and Cmax on Day 1] on linear and semi-logarithmic scales. The accumulation ratio will also be listed and summarized along with other PK parameters.

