Descriptive Summary Statistics	
Continuous Data	Refer to IDSL Statistical Principle 6.06.1
Categorical Data	N, n, frequency, %
Graphical Displays	

 
• Refer to IDSL Statistical Principals 7.01 to 7.13.
 
	
Plasma GSK3640254 concentrations and PK data	

 
• Will be summarized by treatment and listed by participant. Unless stated otherwise, descriptive summaries will include number (n), mean, standard deviation (SD), coefficient of variation (%CV), median, minimum, and maximum for continuous variables, n and percent (%) for categorical variables, and geometric mean, 95% confidence interval (CI), and the between-participant CV (%CVb) for the log-transformed PK parameters.
 
	
Between-subject coefficient of variation (%CVb)	

 
• Untransformed Data: <math>100 * (SD/Mean)</math>
 
• Transformed Data: <math>100 * (\sqrt{\exp(SD_{\log}^2)-1})</math>, where <math>SD_{\log}</math> indicates the standard deviation of log-transformed data.
 
• Within subject coefficient of variation (%CVw) will be calculated according to the following method:  <math>CVw(\%) = \sqrt{\exp(MSE) - 1} \times 100</math> and MSE is the residual mean squared error from the model.            CVw represents a pooled measure of within-subject variability across the treatments.
 
	

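### The fallback dose-proportionality ANOVA omits subject in the Part 1 crossover, which widens the within-cohort intervals, and sets a 3 mg reference that Part 2 never gave (minor)

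*SAP*

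**What the plan says.** SAP 2.3 describes Part 1 as a four-period design in which participants "will be assigned to 1 of the 4 treatment sequences in a cross-over, and each participant will receive placebo once". Each participant therefore takes three active doses. Cohort 1 received 1, 10, 100 and 400 mg; for the other cohort, "Cohort 2 doses are 3 mg, 30 mg, 200 mg, and 700 mg". Part 2 gave 50, 100, 200 and 320 mg to separate groups.

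The main dose-proportionality analysis in SAP 8.1.4.1 respects the crossover: "For Part 1, a power model with subject as the random effect will be fitted". The accumulation analysis in the same section does likewise: "An ANOVA with a random effect term for subject and fixed effect terms for day will be performed by dose".

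The fallback does not. Proportionality "may be assessed by pair-wise analysis of variance (ANOVA) using the SAS Mixed model procedure if power model does not show dose proportionality". One paragraph and one block of example code serve both parts. The class statement lists treatment only, the model is "model logdnPKvar = treatment/ddfm=kr", and there is no random statement. The prose mentions no subject term either. On the reference it says: "A reference dose of 3 mg for all parts, and will be used and the other doses would be treated as test dose". SAP 11.12.7 plans the ANOVA output as Table 4.5 (Part 1) and Tables 4.11 and 4.12 (Part 2, Days 1 and 14).

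**The concern.** In Part 1, any two doses of one cohort are given largely to the same people, and a model with treatment alone treats those repeated measurements as independent. Its residual contains the between-participant variance, which largely cancels when a participant is compared with himself or herself. The intervals for within-cohort contrasts are then wider than the data warrant, and the fallback handles the same crossover data differently from the model it follows.

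In Part 2 the omission of subject is right, because each participant takes one dose and the days are analysed separately. The fault there is the reference: no Part 2 group received 3 mg, so the contrasts have nothing to refer to.

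At stake is the reporting of dose proportionality, a secondary objective. Dose escalation used a separate Bayesian model (SAP 3.1).

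**Working it through.** The documents state no precision for this ANOVA, so there is no figure to reproduce.

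**Inputs**
- Layout (SAP 2.3; protocol 5.1): 2 cohorts × 4 sequences × 2 participants = 16; 16 × 3 active doses = 48 observations, 6 per dose. Any two doses of one cohort share 4 participants. Doses of different cohorts share none.
- Geometric means and CVs (protocol 3.2.2, Table 3). Cmax CVs are 16, 31, 30, 21, 72, 27, 50 and 44%. AUC CVs are 29, 19, 26, 67, 41, 52 and 50% (1 mg not computed).
- Within-participant CV: not in the documents; assumed 15%, 25% or 35%.

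**Step 1. Total log variance.** The mean of ln(1 + CV²) is 0.1418 for Cmax (CV 39%) and 0.1672 for AUC (CV 43%).

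**Step 2. As coded.** SE = √(2 × variance / 6): √(0.1418/3) = 0.217 for Cmax and √(0.1672/3) = 0.236 for AUC. The 90% limits are the estimate divided and multiplied by exp(1.684 × 0.217) = 1.44 (40 df) and exp(1.690 × 0.236) = 1.49 (35 df).

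**Step 3. With subject.** Each cohort is a balanced incomplete block layout: 4 doses, 3 per participant, each pair of doses together in 4 participants. The within-participant variance of a contrast is 2 × 3 / (4 × 4) × ln(1 + CVw²) = 0.375 × ln(1 + CVw²).
- 15%: √(0.375 × 0.0223) = 0.091
- 25%: √(0.375 × 0.0606) = 0.151
- 35%: √(0.375 × 0.1156) = 0.208

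A random subject effect also recovers some between-participant information. This gives 0.091, 0.149 and 0.201 for Cmax, and 0.091, 0.149 and 0.203 for AUC.

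For the cross-cohort 400/3 contrast the SE with subject is 0.195 to 0.216 for Cmax (0.217 as coded) and 0.211 to 0.232 for AUC (0.236 as coded), so little changes.

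**Step 4. The planned contrasts.** The dose-normalised Cmax ratio 700/3 is (1760.8/700)/(13.8/3) = 0.55; the others follow the same form. The with-subject columns keep the Table 3 ratio as the estimate and use 26 df (Cmax) or 21 df (AUC).

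| Contrast | Ratio | 90% CI as coded | With subject, CVw 15% | 25% | 35% |
|---|---|---|---|---|---|
| 700/3 Cmax | 0.55 | 0.38–0.79 | 0.47–0.64 | 0.42–0.70 | 0.39–0.77 |
| 700/3 AUC | 0.50 | 0.34–0.75 | 0.43–0.59 | 0.39–0.65 | 0.36–0.71 |
| 200/3 Cmax | 0.63 | 0.44–0.91 | 0.54–0.73 | 0.49–0.81 | 0.45–0.89 |
| 200/3 AUC | 0.66 | 0.44–0.985 | 0.56–0.77 | 0.51–0.85 | 0.47–0.94 |

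All four exclude 1 in every column.

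**Step 5. Coverage.** Simulations used five of the within/between CV pairs that the protocol uses for planning, with 40,000 runs each. The nominal 90% interval for 700/3 as coded covers about 95% when the two CVs are equal and about 98% when the between-participant CV is twice the within-participant CV. For 400/3 it covers 89–90%.

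**Step 6. Is the fallback likely to run?** A log-log fit to the Table 3 means gives slopes of 0.926 for Cmax (90% CI at widest 0.88–0.97) and 0.902 for AUC (0.84–0.96). Both exclude 1.

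**Step 7. Part 2.** The doses were 50, 100, 200 and 320 mg, and the stated reference is 3 mg. Scaling values to 3 mg is possible arithmetically, but the treatment variable has no 3 mg level to contrast with, so Tables 4.11 and 4.12 cannot be produced as described.

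**The case against.** The fallback is optional, the study tests no formal hypotheses (SAP 2.4), and the code is labelled an example. Its comment assumes four test treatments, which fits neither part, so a programmer would have to adapt it anyway. The error is conservative. Dose-normalised plots and by-dose summaries of log-transformed parameters are planned besides. All of this stands and keeps the point small. It does not remove it, because the prose gives no subject term that would correct the code, and no reading of it supplies a Part 2 reference.

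The layout is also only nominal. Replacements may enter mid-sequence, and the Amendment 04 rationale counts 17 SAD participants with adverse events against 16 planned. Fewer shared participants would shrink the gain somewhat.

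Three stronger readings are tempting but unsupported:
- **A real top-dose departure would be missed.** The contrasts the SAP plans, 700/3 and 200/3, exclude 1 as coded on the preliminary data. A 700/200 AUC interval would include 1 as coded (0.51–1.13), but the SAP plans no such contrast.
- **The top doses are left without a direct contrast.** Both 400 and 700 mg are contrasted with 3 mg. What is absent is a contrast between neighbouring top doses, which neither document promises.
- **A wrong within-participant CV will be reported.** SAP 11.5.2 says "CVw represents a pooled measure of within-subject variability across the treatments", and this residual would not be that. But 8.1.4.1 commits to an intra-subject CV only for the power model; for the ANOVA it commits to point estimates and intervals.

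**Conclusion.** The point holds and is minor. Two things are wrong as written: the Part 1 ANOVA ignores the crossover, and the Part 2 ANOVA names a reference dose that was never given.

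In Part 1 the cost is precision on within-cohort contrasts. The 90% limits are a factor of 1.44 (Cmax) or 1.49 (AUC) either side of the estimate, where about 1.17 to 1.42 would do. False positives are not inflated, cross-cohort contrasts are barely affected, and on Table 3 the conclusions for 700/3 and 200/3 mg do not change.

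These sizes rest on the planned 16-participant layout, on CVs of 16–72% pooled into one variance, and on an assumed within-participant CV of 15–35%. The direction of the error does not depend on the CV chosen, provided there is some between-participant variance.

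**What to change.** In SAP 8.1.4.1, under the ANOVA model:
- **Part 1:** add subject to the class statement and as a random effect, as the accumulation analysis already does.
- **Part 2:** keep the treatment-only model, but name a reference dose that was given, such as 50 mg. Write the estimate statements for the actual number of doses in each part.
- **Table 4.5:** mark each row referenced to 3 mg as within cohort (30, 200, 700 mg) or across cohorts (1, 10, 100, 400 mg), since the two kinds differ in precision.

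Contrasts of 700/200 and 400/100 mg are optional. If added, note that by design each rests on four participants with both doses, that dose is confounded with period within a cohort, and that neither compares 400 with 700 mg.

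The cost is a few lines of specification and a footnote, with no new data.
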